4.3.1.4. Adverse Drug Reaction

An AE will be counted as an ADR if the Clinical Investigator answered “Related” to the AE eCRF question “Relationship to Study Drug?”

4.3.1.5. Events of Special Interest

Events of special interest (ESIs) such as pregnancy, study medication administration error and ocular telangiectasia and bleeding will be identified throughout the study.

4.3.2. Safety Measures

[Table 2](#) below lists the safety measures to be evaluated in this study.

Table 2: Safety Measures

Safety Measure	Note
Best-corrected visual acuity	BCVA measures the acuteness or clearness of the best-corrected vision, with a range of [0, 97] in ETDRS letters. An increase in BCVA indicates an improvement in the best-corrected vision.
Slit-lamp biomicroscopy findings: lid Redness, lid edema, conjunctival hyperemia, conjunctival Edema, corneal edema, anterior chamber cells, anterior chamber flare	Anterior Chamber Cells will be graded as 0 = No cells, 0.5 = 1-5 cells, 1 = 6-15 cells, 2 = 16-25 cells, 3 = 26-50 cells, or 4 = >50 cells. Anterior Chamber Flare will be graded as 0 = None, 1 = Faint, 2 = Moderate, 3 = Marked, or 4 = Intense. The other six biomicroscopy parameters will be graded as 0 = None, 1 = Mild, 2 = Moderate, or 3 = Severe.
Iris	The iris status of an eye will be graded as either Normal or Abnormal.
Lens description	The lens of an eye will be classified as phakic, aphakic, or pseudophakic.
Phakic lens severity score	The status of a phakic lens will be graded as 0 = None, 1 = Mild, 2 = Moderate, or 3 = Severe.
Intraocular pressure	IOP, the fluid pressure inside the eye, is recorded in mmHg. The IOP of an eye is derived as the mean/median of two or three consecutive IOP measurements. In this study, the IOP increase of ≥ 10 mmHg from baseline needs to be reported as an AE.

Table 2: Safety Measures (Continued)

Indirect Ophthalmoscopy findings: cup/disc ratio, retina, macula and choroid, vitreous	Cup/disc ratio will be recorded with two decimal points (e.g., 0.80). Retina (including macular) and choroid will be graded as either Normal or Abnormal. Vitreous haze will be graded as: 0 = Clear, Trace or 0.5+ = Trace, 1+ = Few opacities, mild blurring, 2+ = Significant blurring but still visible, 3+ = Optic nerve visible, no vessels seen, and 4+ = Dense opacity obscures the optic nerve head.
Fundus Photography	Optic disc, Macula.
Fluorescein Angiography	Optic disc, Macula.
Laboratory assessments: hematology, chemistry and urinalysis	Refer to Section 21.4.15 of the protocol for the list of the minimum blood parameters and urine parameters.
Vital signs: systolic blood pressure, diastolic blood pressure, heart rate	For systolic blood pressure (mmHg), if two measurements collected at a visit differ by 5 mmHg or less, then the average of the two will be used as the recorded pressure; otherwise, a third measurement will be taken and the average of the three will be used as the recorded pressure. Same rules apply to diastolic blood pressure (mmHg). The average of the two (or three, if performed) heart rate measurements will be used as the recorded heart rate (beats per minute).

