7.6.2. Treatment/follow-up phase

7.6.2.1. Visit 1 (Day 1)

- Review results of the following procedures performed at Screening (Day -7 to Day -1) to determine continuation in the study:

- Physical exam
- EKG
- Urinalysis
- Blood chemistry and hematology tests
- Serum pregnancy test (for females of child-bearing potential)
- If the subject continues to be eligible for the study, the following assessments must be performed prior to administration of DE-122 to confirm eligibility and obtain baseline characteristics:
 - Query for AEs
 - Update medical history and medications
 - Vital signs
 - BCVA (ETDRS)
 - Slit-lamp biomicroscopy
 - IOP
 - Indirect ophthalmoscopy
 - SD-OCT
 - Immunogenicity serum sample
 - Biomarker serum sample (in Cohorts 3 and 4)
- Perform final review of inclusion/exclusion criteria. If the subject meets all eligibility criteria, determine the study eye ([Section 14.1.5](#)), and then perform DE-122 administration.
- The following procedures must be performed for DE-122 administration ([Section 10](#)):
 - Prepare the DE-122 ([Section 10.4](#))
 - Load the syringe ([Section 10.5](#))
 - Prepare the eye including ocular antisepsis of study eye ([Section 10.6](#))
 - Administer DE-122 ([Section 10.7](#))
- The following assessments must be performed after the administration of DE-122:
 - Within 30 minutes following DE-122 injection
 - Slit-lamp biomicroscopy
 - Indirect ophthalmoscopy
 - IOP 40 (± 10) minutes following DE-122 injection
 - If post-injection IOP is increased ≥ 10 mmHg from pre-injection IOP, the IOP will be measured again 60 (± 10) minutes following injection. If there

is an increase of ≥ 10 mmHg at 60 (± 10) minutes post-injection compared to pre-injection IOP, the subject should be prescribed a topical IOP-lowering medication and monitored for resolution of the event by the Clinical Investigator. An IOP increase of ≥ 10 mmHg shall be reported as an AE.

- AE assessments must be performed after the DE-122 administration
- Upload all collected images (SD-OCT) to sponsor.
- Schedule the subject to return for Visit 2 (Day 2).

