11.2.6. Intraocular Pressure

IOP will be measured by applanation tonometry and reported in millimeters of mercury (mmHg) at each study visit. On the visit of DE-122 or anti-VEGF injection, IOP will be measured before DE-122 or anti-VEGF injection and 40 (±10) minutes after injection. If post-injection IOP is increased ≥ 10 mmHg from pre-injection IOP, the IOP will be measured again 60 (±10) minutes following injection. If there is an increase of ≥ 10 mmHg at 60 (±10) minutes post-injection compared to pre-injection IOP, the subject will be prescribed a topical IOP-lowering medication until he or she returns for follow-up per the Clinical Investigator's discretion (an unscheduled visit may apply), and the IOP increase of ≥ 10 mmHg shall be reported as an AE.

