4. DEFINITIONS

4.1. Time-Related Terms

4.1.1. Baseline Visit

For this study, the *baseline visit* is the Day 1 visit when the injection of DE-122 is scheduled.

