4.2.2. Baseline Score

For any measure, the *baseline score* is the last observed measurement prior to the injection of study medication. For this study, the baseline score would be the measurement prior to the initial injection at baseline visit.

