4.2.4. Change after Injection

For any measure assessed pre- and post-injection at Baseline, the change after injection will be derived as:

Change after Injection = Post-Injection Score – Pre-Injection Score.

The last pre-injection score and the first post-injection score will be used to derive the change after injection variable.

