8.4. Intraocular Pressure

IOP scores and changes from baseline in IOP will be summarized by dose level and analysis visit. Subjects with an increase of \geq 10 mmHg from baseline in IOP will be listed by dose level and subject ID.

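### The SAP ties the ≥10 mmHg IOP adverse-event rule to Day 1 baseline, but the protocol uses same-visit pre-injection IOP; the two differ at anti-VEGF injections, and post-injection readings are not secured for the SAP listing

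*SAP*

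**What the plan says.** **Protocol.** Section 11.2.6, repeated in Appendix D (21.4.7), has IOP measured before each DE-122 or anti-VEGF injection and again at 40 (±10) minutes. If IOP has risen by at least 10 mmHg from the pre-injection value, it is measured again at 60 (±10) minutes. The condition that leads to AE reporting there is: "If there is an increase of ≥ 10 mmHg at 60 (±10) minutes post-injection compared to pre-injection IOP". The visit sections (7.6.2.1, 7.6.2.3, 7.6.2.5, 7.6.2.7) describe the same sequence but put the reporting duty in a separate sentence: "An IOP increase of ≥ 10 mmHg shall be reported as an AE".

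**SAP.** Table 2 in section 4.3.2 restates the rule: "the IOP increase of ≥ 10 mmHg from baseline needs to be reported as an AE". Section 8.4 lists subjects with a rise of at least 10 "mmHg from baseline in IOP will be listed by dose level and subject ID". Section 4.2.2 fixes the reference: "the baseline score would be the measurement prior to the initial injection at baseline visit". Section 4.1.1 says the baseline visit "is the Day 1 visit when the injection of DE-122 is scheduled". The SAP has one pre/post-injection variable, in section 4.2.4, and its scope is Day 1 only: "For any measure assessed pre- and post-injection at Baseline, the change after injection will be derived as" the difference between the post- and pre-injection scores. No analysis in SAP section 8 uses it.

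**The concern.** After Day 1 the protocol and the SAP use different reference readings for the same 10 mmHg threshold. A subject whose resting pressure has drifted since Day 1 can meet one rule and not the other, in either direction.

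Safety and tolerability is the primary objective, and IOP is a named safety measure (SAP 2.1). The trial has about 12 subjects, 2 or 3 per cohort, and no statistical hypothesis, so individual listings carry much of the safety evidence. One subject wrongly absent from or present in a listing is a third or a half of a cohort. A listing built on a different reference also cannot be used to check that the rises the protocol wants reported were in fact reported.

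**Working it through.** The documents give no figure to reproduce: no hypothesis is defined, the sample size has no statistical basis, and no IOP variability is stated. The check compares the two rules and then applies both to cases.

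**1. Where the references can differ.** Let B be the Day 1 pre-injection IOP, P the pre-injection IOP at a later injection visit, and Q the post-injection IOP at that visit.

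- Protocol rise = Q − P (11.2.6).
- SAP rise = Q − B (4.2.2, 4.2.3, 8.4).
- SAP rise − protocol rise = P − B.

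At Visit 1, P = B and the rules agree. DE-122 is given only then. Later injections are anti-VEGF: rescue at Visit 3, or treatment at Visit 5 if there was no Visit 3 rescue, and possibly rescue at Visit 7 (Protocol 9.2.2, 9.2.3). That is at most two per subject.

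**2. Cases (mmHg).**

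| B | P | Q | Protocol rise | SAP rise | Result |
|---|---|---|---|---|---|
| 18 | 18 | 29 | 11 | 11 | both rules met |
| 18 | 12 | 23 | 11 | 5 | protocol rule met, absent from SAP listing |
| 12 | 17 | 23 | 6 | 11 | protocol rule not met, in SAP listing |

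The disagreement follows from the definitions and needs no assumption.

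**3. How often (illustrative only).** Assume each visit's resting IOP varies independently with within-subject SD s. Then P − B is Normal with mean 0 and SD √2·s. For a true post-injection rise r ≥ 10, the probability that the SAP rule misses it is Φ(−(r − 10)/(√2·s)).

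| True rise | s = 1.5 | s = 2.5 | s = 3.5 |
|---|---|---|---|
| 12 | Φ(−0.943) = 17% | Φ(−0.566) = 29% | Φ(−0.404) = 34% |
| 15 | Φ(−2.357) = 1% | Φ(−1.414) = 8% | Φ(−1.010) = 16% |
| 20 | under 0.1% | Φ(−2.828) = 0.2% | Φ(−2.020) = 2% |

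By symmetry, a rise of 8 mmHg appears in the SAP listing without meeting the protocol rule 17%, 29% and 34% of the time. The 6 mmHg fall in the second case of step 2 is itself uncommon: Φ(−6/(√2·2.5)) = Φ(−1.697), about 4.5% at s = 2.5.

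**4. Whether post-injection readings enter the listing at all.**

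- SAP 4.2.3 defines change from baseline at a post-baseline visit. The Day 1 post-injection readings belong to the baseline visit, so read strictly they fall outside it. Only the unused variable in 4.2.4 would hold them.
- At Visits 3, 5 and 7, the selection rule in SAP 4.1.3 chooses between readings by distance in days. It cannot choose between a pre- and a post-injection reading on the same day.
- SAP 4.1.4 leaves analysis timepoints to the ADaM specifications.
- The variable in 4.2.4 takes the first post-injection score, normally the 40-minute one, whereas Protocol 11.2.6 attaches the AE to the 60-minute comparison.

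The SAP text therefore does not guarantee that any post-injection reading, including the one after DE-122, reaches the 8.4 listing.

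**The case against.** The strongest reply is that little of substance is lost, and several parts of it stand.

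- **AE capture.** A reader might infer that IOP adverse events would drop out of the results. The documents do not support that. Investigators record AEs on the eCRF under the protocol (11.1.1.2), and SAP 8.1 tabulates those records. Nothing in 8.1 derives AEs from Table 2 or from 8.4.
- **Study drug.** A reader might infer that the SAP uses the wrong reference for the DE-122 injection. It does not, because at Visit 1 the pre-injection reading is the baseline. What remains open there is only whether the post-injection reading is included.
- **False flags.** A reader might call the extra listed subjects false positives. That goes too far. Protocol 11.1.1 treats any significant adverse change from baseline as an AE, subject to its exception for pre-existing conditions. The dose-limiting IOP criterion in 7.4.1 also refers to baseline. A from-baseline listing is legitimate in its own right.
- **Percentages.** The 17–34% range rests on an assumed SD and on rises placed 2 mmHg from the cut-off. It is not an estimate of impact in this trial.
- **Existing listings.** Protocol 14.1 lists all parameters and SAP 6 provides data listings, so about 12 subjects could be compared by hand. This is true, but raw listings do not correct a misstated rule or the content of the planned 8.4 listing.
- **The 40- versus 60-minute wording.** In the visit sections the AE sentence directly follows the 60-minute sentence, so the natural reading agrees with 11.2.6. This is a minor point of wording.

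**Conclusion.** The point holds within limits. SAP Table 2 misstates the reference for the protocol's IOP AE rule, and SAP 8.4 builds its listing on that reference. The consequence is confined to anti-VEGF injections at Visits 3, 5 and 7, at most two per subject. There the listing can omit rises that meet the protocol's specific rule and include rises that do not, although the latter may still be AEs under the general definition. The AE tables are not affected.

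A second gap is that the SAP does not secure any post-injection reading for the listing, Day 1 included.

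Both conclusions rest on the text alone. The frequency of disagreement cannot be determined from the documents. The illustrative figures are 17–34% for rises 2 mmHg from the cut-off at an assumed SD of 1.5–3.5 mmHg, falling quickly for larger rises. The correction is worth making because it concerns a primary safety measure in a very small trial and uses readings already collected.

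**What to change.** 1. Reword the IOP entry in SAP Table 2 so that the rise is stated against pre-injection IOP at the same visit, as in Protocol 11.2.6.
2. Extend the change-after-injection variable in SAP 4.2.4 to every injection visit (1, 3, 5 and 7), deriving it separately for the 40- and 60-minute readings.
3. Add to SAP 8.4 a listing of subjects with a rise of at least 10 mmHg from same-visit pre-injection IOP, showing the two readings separately.
4. Keep the from-baseline listing as a separate, labelled output.
5. As a minor point, reconcile the wording of Protocol 7.6.2 and 11.2.6 on which reading the AE sentence refers to.

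The cost is SAP wording and one extra listing, with the small protocol wording point in item 5. No new data are needed.

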7.5. Criteria for Study Termination

Unacceptable safety signals that prevent moving to the next higher dose cohort or result in stopping the study may include any of the following, if deemed to be related to study drug DE-122 (not DE-122 administration procedures):

- Pattern of systemic AEs
- Any of the following AEs in any 2 subjects in any cohort:
 - Retinal Non-perfusion of the study eye/vascular occlusion
 - Vasculitis
 - Retinitis
 - > 2+ disc edema
 - > 2 quadrants of retinal hemorrhage

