8.1. Subject Inclusion Criteria

At Screening (Day -7 to Day -1) and Visit 1 (Day 1), subjects must meet all of the following inclusion criteria:

1. Provide signed written informed consent on the IRB / EC approved ICF and provide authorization as appropriate for local privacy regulations.
2. Male or female 50 years of age or older on the date of signing the ICF and able and willing to comply with all treatment and follow-up study procedures.
3. Diagnosis of subretinal or intraretinal fluid secondary to exudative AMD as assessed by SD-OCT in the study eye with a minimum of 300 μm in the central subfield.
4. Prior treatment in the study eye with any intravitreal anti-VEGF medication within the past one year prior to Screening visit (at least 3 anti-VEGF treatments within 6 months or 6 anti-VEGF treatments within 12 months).
5. Treatment with intravitreal injection of anti-VEGF > 30 days and < 60 days from Visit 1 (Day 1).
6. Clinical examination or imaging shows persistent or increasing lesion activity (intraretinal or subretinal fluid, exudation, or hemorrhage) despite continuous anti-VEGF therapy.
7. Total lesion size of ≤ 12 disc areas, contain $\leq 50\%$ hemorrhage and $\leq 50\%$ fibrosis and $\leq 50\%$ retinal pigment epithelial atrophy in the study eye.
8. BCVA of 65 to 20 ETDRS letters (20/50 to 20/400) in the study eye.
9. Fellow eye must have BCVA equal to or better than the study eye, but not worse than 35 ETDRS letters (20/200)
10. Reasonably clear media and some fixation in the study eye to allow for good quality SD-OCT and fundus photography.

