14.1.3. Statistical Hypotheses and Level of Significance

No statistical hypothesis is defined for this study.

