14.7. Safety Analysis

All safety outcome measures will be summarized descriptively for the Safety Population. The safety outcome measures include adverse events (AEs), BCVA, slit-lamp biomicroscopy, indirect ophthalmoscopy, intraocular pressure (IOP), serum chemistry, hematology, urinalysis, vital signs, physical exam, fundus photography, fluorescein angiography, EKG and pregnancy.

AEs will be coded using the Medical Dictionary for Regulatory Activities (MedDRA).

Subjects with any AEs will be tabulated by system organ classification and preferred term specified in the MedDRA. Similarly, subjects with any ocular and non-ocular AEs and ESIs will be tabulated separately. AEs, ocular and non-ocular, as well as ESIs will also be summarized by relationship to treatment and maximum severity. In addition, SAEs and discontinuations due to AEs will be summarized.

Ocular safety outcome measures will be summarized using descriptive statistics.

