3.3. Sample Size Planning

Approximately 12 subjects (2 or 3 subjects in Cohort 1; 3 subjects in Cohorts 2, 3, and 4) with refractory exudative age related macular degeneration will be enrolled at 5 sites. The final number of subjects enrolled may be adjusted based on the presence of dose limiting toxicities

This sample size is not planned based on statistical considerations.

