8. SAFETY ANALYSES

The safety-related measures collected in this study include AEs, BCVA, slit-lamp biomicroscopy variables, IOP, indirect ophthalmoscopy variables, laboratory tests (hematology, chemistry, and urinalysis), vital signs, physical exam, and EKG. The Safety Population will be used for all safety summaries performed with subjects as treated.

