8.5. Ophthalmoscopy

The cup/disc ratio, retina, macula and choroid, as well as vitreous scale will be summarized by dose level and analysis visit.

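### In study eyes the Normal/Abnormal retina grade is expected to start at Abnormal, so the SAP 8.5 summary cannot show worsening, and SAP 8 specifies no analysis of fundus photography or angiography

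*SAP*

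**What the plan says.** **Grade.** SAP 4.3.2, Table 2: "Retina (including macular) and choroid will be graded as either Normal or Abnormal". Protocol Appendix D, 21.4.8, defines abnormal as the presence of a clinically significant abnormality, makes no exception for disease already present, and has a description of each abnormality noted. Each eye is examined at every visit.

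**Planned output.** SAP 8.5, in full: "The cup/disc ratio, retina, macula and choroid, as well as vitreous scale will be summarized by dose level and analysis visit". It mentions no change from baseline, no shift table and no listing, and does not say which eye is covered.

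**Eligibility.** Protocol 8.1, criterion 3: "Diagnosis of subretinal or intraretinal fluid secondary to exudative AMD as assessed by SD-OCT in the study eye", with at least 300 µm in the central subfield. Criterion 6 adds persistent or increasing lesion activity despite anti-VEGF therapy.

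**Imaging.** The safety measures that Protocol 14.7 says will be summarised end with "physical exam, fundus photography, fluorescein angiography, EKG and pregnancy". SAP 2.1 and SAP Table 2 also name both imaging measures, but Table 2 gives only the two anatomical fields. SAP 8 opens: "The safety-related measures collected in this study include AEs, BCVA, slit-lamp biomicroscopy variables, IOP, indirect ophthalmoscopy variables, laboratory tests", then adds vital signs, physical exam and EKG. Neither imaging measure is in that list or in 8.1 to 8.7.

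**The concern.** Safety is the primary objective, and the retinal events that bear on dose adjustment and termination (Protocol 7.4.1 and 7.5) are posterior-segment findings, such as "Retinal Non-perfusion of the study eye/vascular occlusion". Ophthalmoscopy, photography and angiography are the examinations that look at the retina directly. If the ophthalmoscopy grade is already at its worst level before injection, an unchanged column of Abnormal entries says nothing about new toxicity, yet a reader of the study report could take it as reassurance. If photography and angiography have no defined output, nothing in the planned examination tables makes up for that. With two or three subjects per dose, one finding that is hard to see in the report matters.

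**Working it through.** **No power arithmetic applies.** Protocol 14.1.3: "No statistical hypothesis is defined for this study". SAP 3.3: "This sample size is not planned based on statistical considerations". The check is a count and a side-by-side reading.

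**Step 1. Number of study eyes.** Cohort sizes are 2 or 3, then 3, 3 and 3. 2 + 9 = 11 and 3 + 9 = 12, which agrees with the planned total of approximately 12.

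**Step 2. How many study eyes can worsen on the grade.** Let q be the proportion graded Abnormal at baseline. The expected number able to move from Normal to Abnormal is N × (1 − q), and, treating eyes as independent, the chance that none can is q^N. The documents do not give q. Fluid is established by SD-OCT and the ophthalmoscopic grade is a separate judgement, so q below 1 is shown as an assumption.

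| q (assumed) | Eyes able to worsen, N = 11 | N = 12 | Chance that none can, N = 11 | N = 12 |
|---|---|---|---|---|
| 1.00 | 0 | 0 | 1.000 | 1.000 |
| 0.95 | 0.55 | 0.60 | 0.569 | 0.540 |
| 0.90 | 1.10 | 1.20 | 0.314 | 0.282 |
| 0.80 | 2.20 | 2.40 | 0.086 | 0.069 |

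Even at q = 0.80, that is about two eyes across four dose levels. An eye that starts Abnormal can only stay there or improve.

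**Step 3. Treatment of other measures in the same SAP.**

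| SAP section | Measure | Listing of worsening or increase |
|---|---|---|
| 8.3 | Slit lamp | Yes, 2 units or more |
| 8.3.1 | Iris (also Normal/Abnormal) | Yes, Normal to Abnormal |
| 8.3.2 | Phakic lens | Yes, 2 units or more |
| 8.4 | IOP | Yes, 10 mmHg or more |
| 8.6 | Laboratory tests | Yes, any |
| 8.7 | Vital signs | Yes, any |
| 8.5 | Retina, macula, choroid, vitreous haze, cup/disc ratio | No |

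Copying the iris rule would not be enough, because it needs a Normal baseline. The recorded descriptions are what can show a change.

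**Step 4. Imaging.** Sessions are scheduled at Screening and Days 30, 60 and 90. That is 4 × 11 = 44 to 4 × 12 = 48 sessions of each type, of which 3 × 11 = 33 to 3 × 12 = 36 follow injection. Both measures appear in Protocol 14.7, SAP 2.1 and SAP Table 2, and in none of SAP 8 or 8.1 to 8.7. No variable or grade is defined for either.

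**Step 5. What event reporting covers.** Protocol 7.4.1 and 7.5 describe the named retinal events as adverse events, so once reported they reach the SAP 8.1 tables and listings. Ocular bleeding and telangiectasia have a second route as events of special interest. Non-perfusion or occlusion, vasculitis, retinitis and disc edema do not. Protocol 11.1.1 excludes change judged to continue a documented pre-existing condition, although clinically significant worsening may still count. In eyes with active lesions, whether a finding is recorded as an event can therefore turn on that judgement. The 21.4.8 procedure has no disc edema item; the only disc measure is the cup/disc ratio.

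**The case against.** A reader might infer that posterior-segment toxicity has no working summary, or that the planned tables would look the same if a named retinal event occurred. The documents do not support either. A reported event appears in the adverse event tables by system organ class, preferred term and maximum severity, with ocular events first, and in the by-subject listings. Bleeding and telangiectasia are listed separately. Vitreous haze (0 to 4+), cup/disc ratio, BCVA, CST and macular volume are all summarised.

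Nor can the table read only Abnormal. Fellow eyes are examined, SAP 8.5 is not restricted to study eyes, a study eye could improve, and the fluid criterion does not fix the choroid grade if that is recorded separately. The texts leave unclear whether there is one grade or several.

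It is also too strong to say that imaging has been abandoned. SAP 6 promises listings and summaries of all measures, Protocol 14.1 promises that all parameters will be listed, and with two or three subjects per dose a full listing can be read subject by subject. That stands as far as it goes, but a general promise does not say what is to be summarised when no variable exists. The documents describe image capture and upload, not a reading, so a fix must not assume that graded image data exist.

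Finally, the Safety Review Team reviews safety parameters directly after Visits 3 and 5, so dose decisions do not wait for these tables. That also stands: the gap concerns final reporting.

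**Conclusion.** The point holds as a worthwhile, inexpensive improvement to the SAP. In study eyes the retina (including macula) grade is expected to be at its worst level at baseline in nearly all subjects, so the SAP 8.5 summary is close to uninformative about worsening: 0 of 11 or 12 eyes can shift if all start Abnormal, and about 0.6 to 2.4 if 80% to 95% do. The near-100% baseline rate is an inference from eligibility, not a figure in the documents. Separately, two safety measures that the protocol says will be summarised have no specified analysis. Together these leave the reporting of new retinal findings dependent mainly on whether the investigator records an adverse event. They do not leave the primary objective without posterior-segment outputs, and they do not affect dose-escalation decisions.

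**What to change.** **SAP 8.5.** Add a listing by dose level, subject and eye of any new or worsened retina, macula or choroid finding relative to the pre-injection examination, taken from the recorded descriptions. Add a listing of vitreous haze worsening of 2 or more units, matching SAP 8.3. An eye starting at 2+ or lower that reaches 4+ would be caught, since 4 − 2 = 2. State which eye each table covers, and whether retina, macula and choroid are one grade or several.

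**SAP 8.** Restore fundus photography and fluorescein angiography to the list of measures, with a listing of new findings relative to Screening (the only scheduled pre-injection session) as recorded by the investigator. Flag the event types named in Protocol 7.4.1 and 7.5. Add no separate reader or grading scheme.

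**Cost.** SAP wording and two or three listings. The ophthalmoscopy listings use data that the protocol already has recorded. For imaging, if the case report form holds no finding field, one simple new-finding yes/no item is needed. No visit, procedure or stopping criterion changes.
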